#### 7.1.5 Disability

A substantial disruption of a person's ability to conduct normal life functions.

#### 7.1.6 Protocol Deviation (NIH Definition)

Any change, divergence, or departure from the IRB-approved research protocol.

Version Date: 08/23/2017

#### 7.1.7 Non-compliance (NIH Definition)

The failure to comply with applicable NIH Human Research Protections Program (HRPP) policies, IRB requirements, or regulatory requirements for the protection of human research subjects.

## 7.1.8 Unanticipated Problem

Any incident, experience, or outcome that:

- Is unexpected in terms of nature, severity, or frequency in relation to
  - a) the research risks that are described in the IRB-approved research protocol and informed consent document; Investigator's Brochure or other study documents, and
  - b) the characteristics of the subject population being studied; AND
- Is related or possibly related to participation in the research; AND
- Suggests that the research places subjects or others at a *greater risk of harm* (including physical, psychological, economic, or social harm) than was previously known or recognized.

## 7.2 NCI-IRB AND CLINICAL DIRECTOR REPORTING

## 7.2.1 NCI-IRB and NCI CD Expedited Reporting of Unanticipated Problems and Deaths

The Protocol PI will report in the NIH Problem Form to the NCI-IRB and NCI Clinical Director:

- All deaths, except deaths due to progressive disease
- All Protocol Deviations
- All Unanticipated Problems
- All non-compliance

Reports must be received within 7 days of PI awareness via iRIS.

## 7.2.2 NCI-IRB Requirements for PI Reporting at Continuing Review

The protocol PI will report to the NCI-IRB:

- 1. A summary of all protocol deviations in a tabular format to include the date the deviation occurred, a brief description of the deviation and any corrective action.
- 2. A summary of any instances of non-compliance
- 3. A tabular summary of the following adverse events:
  - All Grade 2 **unexpected** events that are possibly, probably or definitely related to the research;
  - All Grade 3 and 4 events that are possibly, probably or definitely related to the research;

Version Date: 08/23/2017

• All Grade 5 events regardless of attribution;

• All Serious Events regardless of attribution.

**NOTE**: Grade 1 events are not required to be reported.

#### 7.3 DATA AND SAFETY MONITORING PLAN

#### 7.3.1 Principal Investigator/Research Team

The clinical research team will meet on a regular basis when patients are being actively enrolled on the trial to discuss each patient. All data will be collected in a timely manner and reviewed by the principal investigator or a lead associate investigator. Adverse events will be reported as required above. Any safety concerns, new information that might affect either the ethical and or scientific conduct of the trial, or protocol deviations and violations will be immediately reported to the IRB via iRIS. The principal investigator will personally conduct or supervise the investigation and provide appropriate delegation of responsibilities to other members of the research staff.

#### 8 STATISTICAL CONSIDERATIONS

We will estimate the distribution of time from initial presentation with pancreatic tumors to the time that surgery is recommended with a Kaplan-Meier Curve. An age-adjusted comparison between this distribution by mutational status (missense vs non-missense mutation, for example) will be done with a proportional hazards model using the method of Wei, et al. (Wei, L.J., Lin, D.Y., and Weissfeld, L., Regression analysis of multivariate incomplete failure time data by modeling marginal distributions. Journal of the American Statistical Association, 84, 1065-1073, 1989) to account for the lack of independence due to familial correlation.

We will estimate the growth rate in solid pancreatic tumors using linear and nonlinear mixed models (Davidian, M. and Giltinan, D.M., Nonlinear Models for Repeated Measurement Data, Chapman and Hall, New York, 1996). These models will allow for the various sources of correlation due to multiple members in the same family and multiple tumors on the same patient. We will compare the growth rate by mutational status as well as by clinical and imaging characteristics by including these factors as covariates in the mixed models. The choice of the form of the linear or non-linear model will depend on the observed data. We will use a linear mixed model on log-transformed volume data if the volume data appears approximately linear on the log-scale. Otherwise, we will investigate alternative models such as the Gompertz model for tumor growth.

The uptake levels of FDG on PET imaging will be compared between patients who require operative intervention and those who do not in order to determine the predictive value of PET imaging in this patient population. Power is based on comparing mean uptake between these two groups of patients. Based on the VHL patient characteristics collected at the Urologic Oncology Branch, NCI, assuming approximately 17% (52 patients) of the targeted 300 VHL patients screened in this study will have solid pancreatic lesion and 50% (26 patients) of them will require operation, we would have 94% power to detect 1 standard deviation difference in the mean uptake between the two groups. The comparison is based on the two-sample t-test at the 5% significance level.

Version Date: 08/23/2017

Based on our analysis of likelihood of tumor growth or risk of metastasis, data will be analyzed every two years and appropriate revisions will be made to the surgical management guidelines, if indicated by data analysis.

As of February 1, 2011, 40 patients have been enrolled who have undergone all four imaging modalities (CT scan, MRI, 18F-DOPA, 18F-FDG). Only 11 of the 98 lesions (11%) were positive on 18F-DOPA as compared to CT scan. Based on this interim analysis, 18F-DOPA is not likely to be useful for detecting pancreatic neuroendocrine tumors in patients with VHL and as of amendment H this mode of imaging is no longer included in protocol evaluations.

As of April 15, 2014, 129 of 276 patients screened in the study had solid lesions. Of these 129 patients, 24 required operative intervention. FDG-PET detected metastatic disease in 3 patients which were not detected by CT, and found non-neoplastic disease in 4 patients. Hence, FDG-PET was able to find 29% of the surgical patients who either had metastasis not detected by CT or had non-neoplastic disease in which operation could be avoided. Using the method of Agresti-Coull (1998), the corresponding 90% confidence interval is (16.5%, 46%) with width 29.5%. Assume that the true proportion of diagnosis of metastatic as well as non-neoplastic disease by FDG-PET which is not detected by CT is 30%. To reduce the width of the 90% expected confidence interval to 20%, a total of 52 surgical patients are required. Correspondingly, approximately a total of 600 VHL patients need to be screened.

Power calculation for the comparison of tumor growth rates between two groups is based on comparing linear growth on the log-scale. Assuming that approximately 9% (54 patients) of screened VHL patients will present or develop pancreatic tumors which require operation over follow-up, we would have 95% power to detect a 1 standard deviation change in the growth rate between two groups of equal numbers (27 in each group) with a two-sided test the 0.05 significance level. This calculation is based on comparing individually estimated slopes (using multiple follow-up measurements on each subject) with a two-sample t-test. This calculation is only an approximation since power may be slightly reduced due to correlation across multiple individuals in the same family and may be increased due to multiple tumors followed on each patient.

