#### 1 INTRODUCTION

#### 1.1 STUDY OBJECTIVES

## 1.1.1 Primary Objectives

- To identify patients with VHL having pancreatic lesions defined by simple cysts, microcystic adenomas, neuroendocrine tumors and other solid lesions of the pancreas.
- To follow patients with VHL and pancreatic manifestations by serial examination with non-invasive imaging studies consisting of CT scan, MRI scan, PET-CT scan, and as clinically indicated, abdominal ultrasound.
- To determine if FDG and FDOPA PET scans can detect early tumor metastasis, and predict which patients will have tumor progression and require an operation based on uptake status. Note: this objective has been met for FDOPA PET imaging. See section 8.
- For patients with solid lesions of the pancreas, to determine the rate of growth and to correlate the growth rate with clinical measures of disease progression such as symptoms.
- To validate non-invasive imaging methods for differentiating benign solid lesions, such as microcystic adenomas, from lesions with malignant potential, namely pancreatic neuroendocrine tumors.
- To characterize the time from initial presentation with pancreatic tumors to the time that surgery is recommended.

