## 1.2 BACKGROUND AND RATIONALE

Patients with von Hippel-Lindau (VHL), a dominantly inherited familial cancer syndrome [1-6], are at risk for developing pancreatic cysts, microcystic adenomas, and pancreatic neuroendocrine tumors (PNETs) [7-9]. PNETs are detected in 12 to 17% of the patients with VHL and these tumors can behave in a malignant fashion, with up to 17% of patients developing metastatic disease [9, 10]. While these neuroendocrine tumors remain a relatively uncommon cause of death, there is a growing recognition of the potential consequences of these tumors if left untreated [6, 9, 10]. We have described previously our experience with the diagnosis and management of these lesions and have made recommendations regarding resection based on size and location of the primary tumor [9]. While this approach appears to have been successful thus far, it has become increasingly evident that some patients manifest a more aggressive phenotype with respect to their pancreatic lesions. Our recommendations for surgery were based on a retrospective review of VHL patients with PNETs who were managed at the NIH. The primary goal of the present protocol is to follow patients diagnosed with PNET in a prospective fashion and to

Version Date: 08/23/2017

apply these management recommendations in order to offer surgery to patients at a time where it may impact on the course of their disease.

Additionally, it has become evident that some patients may manifest a more aggressive phenotype with respect to their pancreatic lesions [11]. Based on this observation, we have previously conducted a retrospective analysis of germ line mutations in patients with VHL and PNETs in order to determine whether or not particular mutations were associated with a more aggressive phenotype [10]. This preliminary study revealed a potential association between mutations in exon 3 and an increased risk of developing metastatic disease. However, given the small number of patients in the study, statistical significance was not reached. Therefore, one of the secondary end points of the present protocol is to conduct germ line mutation analysis in patients found to have PNETs and to correlate differences in germ line mutations with severity of disease.

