#### 2 ELIGIBILITY ASSESSMENT AND ENROLLMENT

#### 2.1 ELIGIBILITY CRITERIA

- 2.1.1 Inclusion Criteria
- 2.1.1.1 Patients who have been diagnosed with VHL using the following criteria: either germ line analysis (12) or clinical criteria or a family history (8, 12) and who have at least 1 pancreatic manifestation of VHL as documented on any non-invasive imaging study. These manifestations may include:
  - Pancreatic cyst(s)
  - Solid lesions suspicious for microcystic adenoma(s)
  - Solid enhancing lesions suspicious for PNET(s)
  - Any other solid lesion(s) of the pancreas
- 2.1.1.2 Age  $\geq$  12 years of age.
- 2.1.1.3 Patients must be willing to return to NIH for follow-up.
- 2.1.1.4 Patients/parent must be willing and able to sign an informed consent.
- 2.1.2 Exclusion criteria
- 2.1.2.1 Patients unwilling to undergo serial non-invasive imaging.
- 2.1.3 Recruitment Strategies

The study will be posted on the CCR website and on clinicaltrials.gov.

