#### 3.2 FOLLOW-UP EXAMINATIONS

Scheduling of follow up evaluations will be coordinated with UOB and/or NOB as appropriate.

- 3.2.1 Patients who are found to have only cystic disease of the pancreas or who have had surgery and who no longer have PNETs may undergo the following evaluations yearly for 2 years and then every two years if no evidence of malignant disease:
  - MRI, US and CT scan of the abdomen with contrast as indicated
  - metanephrines and normetanephrines
  - Chromogranin A
  - Research blood may be collected during follow up (once a year for patients with solid lesions or every two years for patients with cystic lesion) for correlative studies (validation of biomarkers of disease identified from tumor tissue analysis).

**Note:** Patients may be evaluated on a more frequent basis if they develop symptoms consistent with their cystic disease or have evidence of malignant disease recurrence.

- 3.2.2 Patients with solid lesions of the pancreas that are suspicious for PNETs that have not yet reached size criteria where surgery will be recommended (see below) may undergo the following evaluations yearly:
  - CT scans of the abdomen and pelvis with contrast, as well as an MRI scan of the abdomen.
  - FDG PET and PET-MRI scans –patients with solid lesions will undergo PET imaging as follows: Patients who are enrolled on Amendment F will undergo PET imaging at baseline and at one year. Patients who were enrolled prior to Amendment F will undergo PET imaging at their next imaging time point and again in one year.
  - Metanephrines and normetanephrines
  - Chromogranin A
  - Research blood may be collected during follow up (once a year for patients with solid lesions or every two years for patients with cystic lesion) for correlative studies (validation of biomarkers of disease identified from tumor tissue analysis).

**Note:** Due to the amount of radiation exposure, PET imaging will NOT be performed on children under the age of 18 or pregnant or nursing women.

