#### 3.3 SURGICAL MANAGEMENT

Surgery will be recommended to manage lesions within the pancreas under the following circumstances:

Version Date: 08/23/2017

3.3.1 Patients with cystic disease who develop symptoms attributable to their cysts consisting of pain, early satiety or intestinal obstruction will undergo appropriate management of their cysts by best clinical practice (this may include cystectomy, cyst drainage, or internal bypass).

- 3.3.2 Patients with solid lesions of the pancreas that are thought to be PNETs by non-invasive imaging studies will be considered for surgery if:
  - Their solid lesion is enlarging on serial imaging studies.
  - Their solid lesion is associated with symptoms consistent with a pancreatic neuroendocrine tumor.
  - A solid lesion in the head of the pancreas is  $\geq 2$  cm in size.
  - A solid lesion in the body or tail of the pancreas is  $\geq 3$  cm in size.
- 3.3.3 Patients who present with evidence of a pheochromocytoma or other cardiac risk factors will undergo a cardiac evaluation prior to surgical intervention.
- 3.3.4 Patients will be offered surgical management if they meet one of these criteria and the type of operation will be dictated by best clinical management taking into account the desire to preserve as much normal pancreatic tissue as possible. Approaches to the management of solid lesions of the pancreas can range from simple enucleation to distal pancreatectomy and splenectomy or a pancreatico-duodenectomy. Whenever possible, lesions in the pancreas will be managed by a laparoscopic approach. In all cases, intraoperative ultrasound will be utilized during surgical procedures in order to identify and manage additional lesions, as well as to minimize the risk of injury to vessels or the pancreatic duct.

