#### 6 DATA COLLECTION AND EVALUATION

#### **6.1 DATA COLLECTION**

All data will be kept secure. The PI will be responsible for overseeing entry of data into an in-house password protected electronic system (LabMatrix) and ensuring data accuracy, consistency and timeliness. The principal investigator, associate investigators/research nurses and/or a contracted data manager will assist with the data management efforts. All human subjects personally identifiable information (PII) as defined in accordance to the Health Insurance Portability and Accountability Act, eligibility and consent verification will be recorded. Primary data obtained during the conduct of the protocol will be kept in secure network drives or in approved alternative sites that comply with NIH security standards. Primary and final analyzed data will have identifiers so that research data can be attributed to an individual human subject participant.

Data prior to and during the course of the patient's participation will be collected in order to monitor patient eligibility, non-invasive imaging results, and blood work. If patients require surgery, data from preoperative and postoperative course and toxicities will be collected. Tumors visualized on imaging studies will be measured using bi-dimensional tumor measurements (or other appropriate units of measure) at baseline and at each follow up visit.

**End of study procedures:** Data will be stored according to HHS and FDA regulations as applicable.

Loss or destruction of data: Should we become aware that a major breach in our plan to protect subject confidentiality and trial data has occurred, the IRB will be notified.

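### Time to recommended surgery has no fixed start date; if it starts at first documentation of the tumor, the ordinary Kaplan-Meier curve counts pre-enrolment time as at risk and can err in either direction

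*Combined protocol and SAP*

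**What the plan says.** Section 1.1.1 lists as a primary objective: "To characterize the time from initial presentation with pancreatic tumors to the time that surgery is recommended". Section 8 assigns the estimator: "We will estimate the distribution of time from initial presentation with pancreatic tumors to the time that surgery is recommended with a Kaplan-Meier Curve". It then compares mutation groups on the same time scale with an age-adjusted marginal proportional hazards model that allows for family correlation.

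On who enters, Section 2.1.1 takes patients with VHL "who have at least 1 pancreatic manifestation of VHL as documented on any non-invasive imaging study". The listed manifestations run from cysts to solid enhancing lesions suspicious for a pancreatic neuroendocrine tumor (PNET), with no limit on when or where the lesion was seen. The only exclusion is unwillingness to have serial imaging. Section 1.2 describes the aim as to "follow patients diagnosed with PNET in a prospective fashion".

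Section 3.2 has a follow-up track for "Patients who are found to have only cystic disease of the pancreas" and for patients who have already had surgery. Section 3.3.2 gives the circumstances in which surgery is considered for "solid lesions of the pancreas that are thought to be PNETs by non-invasive imaging studies". Section 6.1 says that data from before and during "participation will be collected in order to monitor patient eligibility, non-invasive imaging results, and blood work". The case report form list in Section 6.2.1 is closed. It includes imaging and operations but no date of recommendation, while management details go in the medical record.

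**The concern.** Presentation can be read in two ways.

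- **Presentation to the study.** There is no time before enrolment, and the estimand is time from enrolment.
- **First documentation of the tumor.** The origin may precede enrolment by an unstated interval.

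Under the second reading, a patient who enrols before any recommendation could not have been observed to have one before enrolment, yet an ordinary curve counts that interval as time at risk. A patient already recommended for surgery may or may not enrol, and Section 8 has no rule for counting one who does. The result depends on how such patients are represented, which the plan does not address.

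This is the only analysis named for the objective. Two analysts following Section 8 could draw different curves from the same records.

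**Working it through.** **No figure to reproduce.** The plan gives no median, event count or power for this endpoint, so the check is an illustration.

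**Input from the documents.** n = 129 patients with solid lesions (Section 8, April 2014). This counts all solid lesions. Section 1.1.1 seeks methods for "differentiating benign solid lesions, such as microcystic adenomas, from lesions with malignant potential, namely pancreatic neuroendocrine tumors", so some solid lesions are benign and the number of suspected PNETs is smaller.

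**Assumptions, not in the documents.** Constant hazard h = 0.05 per year; delay V from first documentation to enrolment uniform on 0 to D years, with D = 2 or 5, or zero for a fraction w of patients; follow-up uniform on 0-8 years after entry; no family correlation.

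**True 5-year value.** 1 - exp(-0.05 x 5) = 1 - 0.7788 = 22.1%.

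**Closed form when nobody with an earlier recommendation enrols.** Ignoring censoring, the ordinary curve estimates P(T <= 5 given T > V) = [w(0.2212) + (1-w)(M - 0.7788)] / [w + (1-w)M], where M = (1 - exp(-hD))/(hD).

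- D = 2, w = 0.5: M = 0.9516, giving (0.1106 + 0.0864)/0.9758 = 20.2%.
- D = 5, w = 0.5: M = 0.8848, giving (0.1106 + 0.0530)/0.9424 = 17.4%. With the assumed follow-up the simulation gives 16.4%, because late entrants make up a growing share of those counted at risk.

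**Simulation: mean ordinary 5-year estimate, truth 22%.** Columns give the share of earlier-recommended patients who enrol and are dated, or how many times as likely as others they are to enrol.

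| Setting | 0% | 25% | 50% | 100% | 2 times | 3 times |
|---|---|---|---|---|---|---|
| Half undelayed, 0-2 y | 20.2 | 20.5 | 21.1 | 22.2 | 24.2 | 26.0 |
| Half undelayed, 0-5 y | 16.4 | 18.0 | 19.4 | 21.9 | 27.1 | 31.4 |
| All delayed, 0-2 y | 18.1 | 19.2 | 20.2 | 22.0 | 25.8 | 29.3 |
| All delayed, 0-5 y | 11.2 | 14.2 | 17.2 | 22.1 | 30.6 | 37.6 |

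Opening the risk set at enrolment (delayed entry) gives 21.8 to 22.4 throughout. A separate run with an assumed median of 20 years and mean lag of 3 years agrees. The true 5-year proportion without a recommendation is 0.841. With independent entry and no earlier recommendations enrolled, the ordinary curve gives 0.914 and delayed entry 0.841. With earlier recommendations over-represented, the ordinary curve gives 0.779.

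**Where delayed entry fails.** Suppose that 25/50/100% of delayed patients whose recommendation falls within 5 years are referred in the 6 months before it (0-5 year delay otherwise).

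| Estimate | Half undelayed | All delayed |
|---|---|---|
| Ordinary | 18.3 / 20.1 / 23.1 | 15 / 18 / 24 |
| Delayed entry | 24.8 / 27.5 / 32.3 | 41 / 55 / 74 |
| Lesion first seen on study | 22.2 / 22.1 / 22.0 | no patients |

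With half undelayed, a 10%-level test of delayed against undelayed patients detects this in only 23/44/81% of runs.

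**Root-mean-square error in points, ordinary v delayed entry, 0-5 years.**

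- Half undelayed, share enrolled 0/50/100%: 6.8 v 4.8, 4.8 v 4.9, 4.3 v 5.0. At 3 times as likely: 10.4 v 5.3.
- Half undelayed, referral 25/50/100%: 5.5 v 5.8, 4.5 v 7.6, 4.5 v 11.7.
- All delayed, share enrolled 0/25/50/100%: 11.3 v 8.3, 8.6 v 8.0, 6.1 v 7.8, 3.8 v 8.5.

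Neither estimator is uniformly better.

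**The case against.** The strongest reply is that no section selects the first-documentation reading. Section 1.2 contrasts a past retrospective review with prospective follow-up, which fits a clock starting at enrolment at least as well. It does not say that the tumor was diagnosed before enrolment, and a qualifying lesion may be only a cyst. This stands, and it makes the bias conditional. It does not remove the problem, because Section 2.1.1 expressly admits a suspected PNET already documented on any imaging, and the text never fixes the date.

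A second reply is that delayed entry can be worse than the plan. This also stands. Section 9.5 lists surgery at an experienced institution as a benefit, so referral prompted by impending surgery is plausible, and delayed entry overshoots in that case. It should not simply replace the ordinary curve.

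Third, the objective is descriptive, no sample size depends on it, and both dates should be recoverable from imaging and the medical record. All true. They limit the weight of the point but do not settle the definition.

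A reader might infer that the planned curve is certainly too optimistic, or that the mutation comparison is biased. The documents support neither. The direction depends on unknown enrolment patterns, and the comparison is affected only if delay or referral differs by mutation group, which no section states.

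**Conclusion.** The concern holds conditionally. The missing origin date, and the missing rule for recommendations made before or at enrolment, are facts of the text. The bias follows only if the origin is first documentation, and it vanishes even then if patients with an earlier recommendation enrol as readily as others and are dated.

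Its size cannot be derived from the documents. Across the assumed enrolment patterns at 5% per year, the ordinary 5-year estimate ranges from 11% to 38% against a true 22%. With half the patients undelayed and delays of up to 2 years, it ranges from 20% to 26%. These values rest on an assumed hazard, delay, referral pattern and follow-up. Precision for suspected PNETs will be lower than n = 129 implies.

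**What to change.** In Section 8:

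1. State the origin date. Define the event per patient as the first recommendation of surgery for any pancreatic lesion thought to be a PNET, since one patient can have several lesions (Section 8 reports 98 lesions where 40 patients had all four scans). Sections 1.2.1 and 3.3.2 must be reconciled first: the former lists abdominal surgery for other VHL manifestations as a circumstance, and the latter does not. Take both dates from imaging and the medical record.
2. If the origin can precede enrolment, report beside the ordinary curve a delayed-entry analysis, in both the Kaplan-Meier curve and the hazards model, with the risk set opening at first registration. Count only later recommendations as events and report earlier ones separately. State how the 2009 off-study gap and re-registration (Section 2.2) are treated.
3. Report the patients whose lesion first appears on study, which needs no assumption about entry, and time from enrolment as a separate estimand. State that delayed entry assumes entry is unrelated to impending surgery and can overshoot otherwise. If the results disagree, report the range and rely on no single curve. A significance test should not be the only check.
4. If enrolment was meant, name the estimand time from enrolment and state how patients already recommended for surgery at entry are counted. Step 2 is then unnecessary.

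**Cost.** A short addition to Section 8, abstraction of two dates for each patient, and wider intervals. Under the assumptions above (n = 129, 0-5 year delay, no earlier recommendations enrolled), the standard deviation of the 5-year estimate in points is:

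| | Ordinary | Delayed entry | On-study lesions |
|---|---|---|---|
| Half undelayed | 3.8 | 4.8 | 6.3 (about 12 events) |
| Quarter undelayed | 3.5 | 5.2 | 8.9 (about 6 events) |
| All delayed | 3.1 | 8.3 | no patients |

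The on-study subset describes tumors found under surveillance and may not represent those found before referral. In April 2014, 276 - 129 = 147 screened patients had no solid lesion. They are the pool in which one could first appear, and the documents do not say how many earlier patients moved from that pool.
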